#### **6.7.1.2 Vital signs**

Descriptive statistics (mean, standard deviation [SD], minimum, maximum, and n) including change from baseline (pre-dose value of the relevant treatment period) for actual values of vital sign parameters will be presented for all scheduled time points by cohort. Additionally, the number of subjects with "substantial" increases or decreases in BP ( $>20$  mmHg) and heart rate ( $>15$  bpm) will be tabulated as shift table. It includes heart rate, systolic and diastolic blood pressures, respiratory rate, and body temperature. Vital signs details will be listed.

#### **6.7.1.3 12-Lead electrocardiograms**

Descriptive statistics (mean, standard deviation [SD], minimum, maximum, and n), including change from baseline (pre-dose value of the relevant treatment period) for 12-Lead Electrocardiograms parameters of heart rate, rhythm, PR, RR, PQ, and QT intervals, QTc [Bazett's and Fridericia's], and QRS will be presented for all scheduled time points by cohort. ECG results will be listed.

#### **6.7.1.4 Clinical laboratory tests**

Descriptive statistics (mean, standard deviation [SD], minimum, maximum, and n), including change from baseline (pre-dose value of the relevant treatment period) for laboratory parameters of hematology, serum chemistry, coagulation, and urinalysis will be presented for all scheduled time points by cohort. Laboratory test results will be listed and abnormal values outside normal ranges will be flagged.

If data permits, urinalysis (pH and specific gravity) will be summarized (mean, SD, median, minimum, maximum, and n) at each time point. Shift tables for laboratory parameters will be generated based on changes in National Cancer Institute Common Terminology Criteria for AE grade from baseline to worst post-baseline value.

#### **6.7.1.5 MRI and X-ray data**

The results of independently evaluated imaging assessments will be provided [REDACTED]. Absolute and change from baseline in MRI and X-ray (including morphological assessment) results will be analyzed for all scheduled time points and cohort using descriptive statistics. MRI and X-ray data will be displayed in subject data listings.

#### **6.7.1.6 Neurologic assessments**

Neurological examination results and change from baseline will be summarized for all scheduled time points by cohort. Information includes: deep tendon reflexes (patellar [or knee], Achilles [or ankle] as normal, decreased, absent, increased or clonus and Babinski's Sign as present, plantar flexion or no response); muscle strength (hip flexion, knee flexion, knee extension, ankle dorsiflexion/long toe extension, ankle plantar flexion as normal, decreased to resistance, against gravity only/no resistance, or no movement); sensory exam to pin-prick (anterior knee, medial malleolus, dorsum of the foot, anterior toes 1-3 and anterior toes 4-5 and lateral malleolus as normal, decreased/abnormal or absent) and overall clinical impression since baseline (as improved, remain unchanged or worsened). Positive straight-leg raising or femoral stretch test will also be summarized. A data listing of neurological evaluations will be provided.

#### **6.7.1.7 Physical examinations**

The number of patients reporting abnormalities for physical examination will be tabulated for all scheduled time points using counts and percentages for each body system. Physical examination results will be displayed in the subject data listings.

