	
Safety endpoints and analysis:
 
The following safety endpoints will be analyzed and presented using descriptive statistics (n, mean, median, minimum, maximum, standard deviation [SD], percentage of analysis population, and confidence interval [CI]):
 
• Adverse events, serious adverse events (SAEs), deaths, or discontinuations due to AEs (including subjects who have lumbar surgery) that occur after administration of study drug. Adverse events will be coded using the Medical Dictionary for Regulatory Activities.• Change and shifts from baseline in vital signs (including heart rate, systolic and diastolic blood pressures, respiratory rate, and body temperature), 12-lead ECGs (including heart rate, rhythm, PR, RR, PQ, and QT intervals, QTc [Bazett's and Fridericia's], and QRS), and clinical laboratory tests (including hematology, serum chemistry, coagulation, and urinalysis).• Change from baseline in MRI and X-ray (including morphological assessment).• Change from baseline in neurologic assessments, including positive straight-leg raising or femoral stretch test, alteration of deep tendon reflexes (knee and ankle), sensory, or motor deficits in the lower extremities.• Clinically significant change from baseline in physical examinations.• Number of subjects who experienced any AEs defined as a halting rule.• Serum anti-KTP-001 antibody analysis [REDACTED].

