9 SAFETY ASSESSMENTS

Unless otherwise noted, the endpoint for all safety assessments is changes from baseline.

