9.2 Clinical Laboratory Tests

Samples will be obtained for the clinical laboratory tests as defined in [Appendix H](#) outlined in the Schedule of Assessments ([Section 11](#)) at screening, at specified times during the study.

A certified central laboratory will be utilized to process and provide results for the clinical laboratory tests. The baseline laboratory test results for clinical assessment for a particular test will be defined as the last measurement prior to the initial dose of study drug.

For any laboratory test value outside the reference range that the investigator considers clinically significant, the investigator will:

- Repeat the test to verify the out-of-range value.
- Follow the out-of-range value to a satisfactory clinical resolution.
- Record as an AE any laboratory test value that (1) is confirmed and the investigator considers clinically significant; or (2) that requires a subject to be discontinued from the study; or (3) that requires a subject to receive treatment.

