9.3 Electrocardiograms

A standard 12-lead ECG will be obtained at screening, and at 24 hours and 13 weeks post-dose.

Additional ECGs may be obtained if clinically indicated. Follow-up ECGs will be obtained if any significant abnormalities are detected after dose administration to document resolution and as clinically indicated. Any additional relevant data obtained by the investigator during the course of this study will be supplied to the Sponsor.

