12.5.4 Electrocardiograms

Descriptive statistics (mean, SD, minimum, maximum, and n) from the 12-lead ECG assessment will be summarized at each time point when the ECG evaluation is performed.

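### The SAP omits two safety summaries named in the protocol synopsis, change from baseline in physical examination and ECG shifts, and gives ECG and laboratory tests a baseline phrase that does not fit the schedule

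*SAP*

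**What the plan says.** **Protocol, endpoints.** The safety endpoints in the synopsis (Section 1) include "Clinically significant change from baseline in physical examinations" and "Change and shifts from baseline in vital signs (including heart rate, systolic and diastolic blood pressures, respiratory rate, and body temperature), 12-lead ECGs"; the second sentence goes on to cover laboratory tests. Protocol Section 9 sets the default: "Unless otherwise noted, the endpoint for all safety assessments is changes from baseline".

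**Protocol, analysis section.** Section 12.5 is narrower than the synopsis. Under 12.5.4, descriptive statistics "from the 12-lead ECG assessment will be summarized at each time point when the ECG evaluation is performed", with neither change nor shift mentioned. Section 12.5.5 plans only a descriptive summary of the abnormal findings noted.

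**SAP.** The endpoint list in 6.7.1 attaches change and shifts to vital signs only. ECG stands as a separate item without those words, and physical examination is listed simply as abnormalities. Section 6.7.1.7 then reads "The number of patients reporting abnormalities for physical examination will be tabulated for all scheduled time points", as counts and percentages by body system, plus a listing. Section 6.7.1.3 gives mean, SD, minimum, maximum and n, "including change from baseline (pre-dose value of the relevant treatment period) for 12-Lead Electrocardiograms parameters"; rhythm is in the same parameter list, and there is no shift table. Section 6.7.1.4 uses the same bracketed baseline for laboratory tests but keeps toxicity-grade shift tables. SAP 9.0 lists only the removal of PK parameters and of rescue-medication counts.

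**Baseline and timing.** SAP 4.0 takes the last result before the first dose, except where another rule is given. Protocol 9.2 says the laboratory baseline "will be defined as the last measurement prior to the initial dose of study drug". Protocol 9.3: "A standard 12-lead ECG will be obtained at screening, and at 24 hours and 13 weeks post-dose".

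**The concern.** Safety and tolerability are the primary objective of this first-in-human study, and SAP 6.7.1 lists both physical examination and ECG among the primary safety endpoints. If the SAP is followed as written, two summaries that the synopsis names will not be produced, and nothing in SAP 9.0 tells the reader so.

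A count of abnormal subjects at each visit does not show whether they are the same subjects who were abnormal before injection. A finding that goes from clinically insignificant to clinically significant does not move the count at all. For ECG, means and extremes describe the size of changes but not how many subjects moved from normal to abnormal. A mean and SD of rhythm cannot be interpreted.

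The baseline phrase is a smaller matter. It speaks of treatment periods in a single-injection study and points to a pre-dose value for tests that the Day 1 pre-dose visit does not include. A programmer who reads it literally could look for a record that does not exist.

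**Working it through.** The documents give no figure on this point to reproduce, so the check is a comparison of texts plus two small illustrations.

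**1. What the synopsis asks for and what the SAP delivers**

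| Domain | Synopsis | Protocol 12.5 | SAP |
|---|---|---|---|
| Vital signs | change and shifts | change, threshold counts | change, threshold counts as a shift table (6.7.1.2) |
| Laboratory | change and shifts | change, grade shifts | change, grade shifts, flagged listings (6.7.1.4) |
| ECG | change and shifts | summary by time point | change, minimum, maximum; **no shift** (6.7.1.3) |
| Physical examination | clinically significant change | summary of abnormalities | visit counts; **no change** (6.7.1.7) |

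The gap is confined to the last two rows. It begins inside the protocol, where Section 12.5 asks for less than the synopsis.

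**2. What an unchanged visit count can conceal**

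Take a cohort of n = 6 with k subjects abnormal in one body system at baseline. The count stays at k if the number of new findings equals the number resolved. New findings can arise only in the 6 − k normal subjects, and resolutions only in the k abnormal ones. The most that can be concealed is therefore min(k, 6 − k).

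| k at baseline | 0 | 1 | 2 | 3 | 4 | 5 | 6 |
|---|---|---|---|---|---|---|---|
| New findings concealed, at most | 0 | 1 | 2 | 3 | 2 | 1 | 0 |

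Example (assumed data): 2/6 are abnormal at baseline, one resolves and one new finding appears. The visit table shows 2/6 and 2/6; a shift table shows 1/6 new.

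**3. ECG illustration (assumed data)**

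One subject changes by +60 ms and five do not change.

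- Mean change = 60/6 = 10 ms.
- SD = √[((60 − 10)² + 5 × (0 − 10)²)/5] = √(3000/5) = 24.5 ms.
- Maximum change = 60 ms.

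With +30 or +45 ms in place of +60, the mean change is 30/6 = 5 ms or 45/6 = 7.5 ms. The mean dilutes the outlier, but the planned maximum shows it. What is absent is the number of subjects who changed category, and any usable summary of rhythm.

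**4. Baseline**

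The Day 1 pre-dose list (Protocol 11.2.1) has vital signs and physical examination, but no ECG and no safety laboratory test. ECGs fall at screening, 24 hours and Week 13. Laboratory draws fall at screening, 24 hours and Weeks 1, 2 and 13 (Protocol 11.1, 11.2.5, 11.3, 11.4, 11.7). That makes 5, which agrees with the 5 samples in Protocol 11.16. The only value before injection is therefore the screening one, up to 21 days old. In the protocol, the treatment-period phrase appears for vital signs (12.5.1), where a Day 1 pre-dose value exists. It is not used in the laboratory or ECG sections (12.5.2, 12.5.4).

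**The case against.** The case on the other side has substance.

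- **The SAP follows the protocol's own analysis section.** This is correct. For ECG it improves on Protocol 12.5.4 by adding change from baseline. The conflict is between the synopsis and Section 12.5, and the SAP took one side without saying so.
- **ECG is not reduced to means.** A reader might infer that a single outlier would vanish into a cohort mean. It would not: the maximum change is in the same table and the results are listed. This protection covers scheduled ECGs only. SAP 4.0 keeps unscheduled measurements out of the descriptive statistics, apart from repeats after a measurement error, so follow-up ECGs prompted by an abnormality would generally appear only in listings.
- **Physical examination counts may start low.** Inclusion criterion 9 requires subjects to be healthy apart from the herniation, and when k = 0 an unchanged count conceals nothing. The criterion still admits clinically insignificant abnormalities, so k need not be 0. Concealment does require equal numbers of new and resolved findings in one body system at one visit.
- **Every subject enters with a positive leg test.** A reader might infer from inclusion criterion 2 that the count would sit at 6/6 throughout. The documents do not support this. Those tests belong to the neurologic examination (Protocol 9.7), which SAP 6.7.1.6 analyses with change from baseline.
- **Other outputs remain.** Listings for cohorts of 6 are readable, and TEAE tables separate new or worsened events. The TEAE route depends on a finding being reported as an adverse event. Protocol 9.2 directs that for confirmed, clinically significant laboratory values; 9.3 and 9.4 contain no equivalent instruction.
- **Rhythm.** SAP 6.7 refers to Section 4.0, which summarises categorical data by counts, so a sensible programmer could recover. The text of 6.7.1.3 still places rhythm under mean and SD.
- **Baseline.** A screening value does precede dosing. A reader might infer that every laboratory grade shift lacks a baseline. It does not: the shift-table sentence in SAP 6.7.1.4 carries no bracket, so SAP 4.0 applies, in agreement with Protocol 9.2.

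**Conclusion.** The point holds in a limited form and should be corrected. Two safety summaries named in the synopsis, clinically significant change in physical examination and ECG shifts, are not planned in the SAP, and SAP 9.0 is silent. The physical examination table cannot separate new from pre-existing findings, with at most 3 of 6 concealed behind an unchanged count. That is a worst case at k = 3, not an expected value. The ECG tables show the size of the largest scheduled change but not how many subjects worsened in category.

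New abnormalities can be obscured in the summary tables; they are not lost from the report. Laboratory and vital-sign change and shift analyses are intact. The baseline bracket is a wording conflict with SAP 4.0 and Protocol 9.2, and a usable screening baseline exists.

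The conclusion rests on cohorts of 6 as planned and on the visit lists in Protocol Section 11. The ECG and 2/6 examples use assumed data.

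**What to change.** 1. **SAP 6.7.1.7:** add a shift table by body system and cohort, from baseline status to worst post-dose status. Give the number of subjects with a new or worsened abnormality, restricted to clinically significant ones where that grading is recorded. Physical examination is done at screening and on Day 1 before dosing, so no new examination is needed.
2. **SAP 6.7.1.3:** add an ECG shift table from baseline to worst post-dose, covering overall interpretation where recorded, rhythm, and QTc categories derived from the collected values. Fix the category limits in the SAP and state whether unscheduled ECGs count towards the worst value. Summarise rhythm by counts.
3. **SAP 6.7.1.3 and 6.7.1.4:** replace the bracketed baseline with *last value before the injection (the screening value under the schedule)*.
4. **SAP 9.0:** record any difference from the synopsis that remains.

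The cost is SAP wording and two additional tables. What they can show depends on the categories the CRF captures. Protocol 9.3 and 9.4 do not specify a normal, abnormal or clinically significant grading, and the CRF was not available to check.

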#### **6.7.1.8 Halting rules**

The number of subjects with AEs defined as halting rules (HRs) will be described and evaluated. Halting rule is explained in the [appendix 4](#).

### **6.7.2 Analysis of Exploratory Efficacy Endpoints**

Exploratory efficacy endpoints analyses will be performed on the full analysis set and per protocol set and all analyses will be presented using descriptive statistics as mentioned in the [section 4](#). For all measures other than the daily pain, the baseline value is defined as the last assessment result collected prior to the first dose of study medication. For daily pain assessments, the baseline value is defined as the average of the results of 5 consecutive days prior to the first dose of study medication.

The following are the primary exploratory efficacy endpoints:

- Change from baseline in lower back pain or leg pain (numerical pain scale for each sub categories as mentioned below) at 6 and 13 weeks

- Leg average daily pain
- Leg worst daily pain
- Low back average daily pain
- Low back worst daily pain
- Current leg pain
- Current low back pain
- Number of subjects requiring:
  - Additional pain medication (and amounts) added to the subject's baseline pain regimen within the first 13 weeks post-dose
  - An epidural injection, a selective nerve root block, or a facet block after receiving study drug,
  - Surgical intervention for lumbar disc herniation
- Change from baseline in spinal flexion and tension signs (straight-leg raising or femoral stretch test) on the affected side at 6 and 13 weeks
- Change from baseline in ODI at 6 and 13 weeks
- Change from baseline in SF-12 at 6 and 13 weeks
- Change from baseline in the PGI-C at 6 and 13 weeks

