5 STUDY DESIGN

5.1 Design Summary

Study KTP-001-CL-101 is an open-label, non-controlled single ascending dose study of KTP-001 in male and female subjects between the ages of 30 and 70 with a single herniated lumbar disc. After obtaining informed consent, subjects will be evaluated during a screening period of no more than 3 weeks (21 days). The following procedures will be performed at the screening visit: collection of subject baseline demographics, medical history (including the symptoms associated with herniated lumbar disc), prior medications, height, weight, a full physical and neurologic examination (including straight-leg raising and femoral stretch test), and collection of vital signs, 12-lead ECG, and clinical laboratory tests (hematology, serum chemistry, coagulation, urinalysis, and urine drug screen). A serum pregnancy test will be conducted for female subjects of childbearing potential. The following baseline exploratory efficacy measures will be assessed: lower back and leg pain using a numerical scale (using a subject diary for 5 consecutive days prior to treatment), spinal flexion/tension using straight-leg raising and femoral stretch test, MRI assessment, lumbar spine X-ray assessment, the severity of disability using the Oswestry Disability Index (ODI), QOL using the Short Form-12 (SF-12) questionnaire, and symptom severity as measured by the PGI-C scale. A pain assessment diary will be administered and collected between screening and treatment on Day 1.

Subjects that meet all screening requirements and inclusion criteria and none of the exclusion criteria will be enrolled into 1 of 4 study cohorts and receive KTP-001. Following administration of study drug, subjects will be confined to the study unit for 24 hours to collect data for safety and efficacy measures and collect blood samples for the following purposes: safety, PK evaluation, and exploratory PD (keratan sulfate), including anti-KTP-001 antibody.

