8 EFFICACY ASSESSMENTS

The following efficacy measures are all exploratory in nature and all analyses will be presented using descriptive statistics. For all measures, the baseline value is defined as the last assessment result collected prior to the first dose of study medication. Unless otherwise noted, the endpoint for all efficacy measures will be changes from baseline at 6 and 13 weeks post-dose.

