8.6 Global Impression of Change or Improvement

Global impression of improvement as measured by the PGI-C ([Appendix G](#)) is a single question survey that will be administered at baseline, on Day 1 pre-dose, at 24 hours post-dose, and at all post-dose visits. The endpoint for global impression of change or improvement will be changes from baseline at 6 and 13 weeks post-dose.

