11.2 Visit 1 (Day 1)

11.2.1 Pre-dose

- Admit to study unit. The subject will be hospitalized for 24 hours after intradiscal injection of the study drug and will be discharged once all procedures are completed and the investigator determines the subject is safe to be discharged.
- Review concomitant and prior medications
- Physical examination including measurement of weight without shoes
- Neurologic examination
- Vital signs (including BP, pulse, respiratory rate, and temperature)
- Urine pregnancy test for women of childbearing potential (result must be negative to continue to be eligible)
- Collect and review Study Diary
- Dispense Study Diary
- Review AEs
- Assess current lower back and leg pain using the 11-point numerical rating scale
- Assess Spinal Flexion/Tension (Straight-leg Raising/Femoral Stretch Test)
- Assess ODI, SF-12, and PGI-C
- Administer study drug
- Draw blood samples for measurement of anti-KTP-001 antibody
- Draw blood samples for measurement of KTP-001
- Draw blood samples for measurement of serum keratan sulfate

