### **Global impression of change or improvement**

Global impression of improvement as measured by the patient global impression of change (PGI-C) is a single question survey that will be administered at baseline, on day 1 pre-dose, at 24 hours post-dose and at all post-dose visits. Visit value and change from baseline in PGI-C score at 6 and 13 weeks will be summarized by cohort. Visit value and change from baseline for other visits also summarized in a separate table same as mentioned above. Listing will be provided for PGI-C score.

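### PGI-C endpoint: if the form rates change, change from the pre-dose score subtracts one change rating from another (minor, exploratory)

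*SAP*

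**What the plan says.** The endpoint is named the same way throughout.

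- SAP 6.7.2 lists "Change from baseline in the PGI-C at 6 and 13 weeks"; the Protocol Synopsis has the same item under its exploratory efficacy endpoints.
- Protocol 8.6: "The endpoint for global impression of change or improvement will be changes from baseline at 6 and 13 weeks post-dose". This repeats the general default in Protocol 8: "Unless otherwise noted, the endpoint for all efficacy measures will be changes from baseline at 6 and 13 weeks post-dose".
- SAP 6.7.2, paragraph on global impression: "Visit value and change from baseline in PGI-C score at 6 and 13 weeks will be summarized by cohort". Other visits go in a separate table, and scores are listed.

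For every measure except daily pain, SAP 6.7.2 says "the baseline value is defined as the last assessment result collected prior to the first dose of study medication". PGI-C is collected at screening (Protocol 11.1) and again before dosing on Day 1, where Protocol 11.2.1 has "Assess ODI, SF-12, and PGI-C". The Day 1 answer is therefore normally the one subtracted.

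The descriptions of the instrument differ. Protocol 2.2 expands PGI-C as an impression of change. Protocol 8.6 and the SAP paragraph call it a single-question survey measuring global impression of improvement. Protocol 5.1, however, lists among the baseline measures "symptom severity as measured by the PGI-C scale", and the efficacy list in the Synopsis speaks of improvement in symptom severity measured by PGI-C.

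**The concern.** A rating of change already contains the comparison with an earlier state. Subtracting a pre-dose rating makes the comparison a second time, and the result depends on what the subject answered before receiving any treatment. The general default in Protocol 8 suits ODI and the pain scales, which measure a current state. It does not suit a change rating.

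The SAP shows another way of presenting such a rating. For the neurologic examination, SAP 6.7.1.6 names an "overall clinical impression since baseline (as improved, remain unchanged or worsened", so the reference point and the categories are both clear. The PGI-C paragraph instead makes a difference in score the endpoint.

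What is at stake is whether the named endpoint can be interpreted. No hypothesis test or dosing decision rests on it.

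**Working it through.** The plan gives no figure for this endpoint, so there is none to reproduce. The check sets out what the named endpoint computes, then how far it can depart from the subject's own rating.

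**Inputs.** Endpoint: post-dose score minus last pre-dose score (SAP 6.7.2; Protocol 8.6). Cohort size: 6 (Protocol Synopsis). Assumed: the form rates change, answers are coded in unit steps with neutral = 0, and data are complete.

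**Step 1, one subject.** Let b be the pre-dose answer and v the post-dose answer. The endpoint is v − b.
- If b = 0, then v − b = v, so the change table repeats the visit-value table.
- If b ≠ 0, subjects with the same v get different endpoint values. With v = +2, a subject with b = 0 scores 2 and a subject with b = +1 scores 1, although both gave the same post-dose answer.

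**Step 2, cohort mean.** mean(v − b) = mean(v) − mean(b). If k of the 6 subjects are one step off neutral in the same direction before dosing, the mean shifts by k/6. This needs no assumption about scale length.

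| k | Shift in cohort mean (steps) |
|---|---|
| 0 | 0 |
| 1 | 1/6 = 0.17 |
| 3 | 3/6 = 0.50 |
| 6 | 6/6 = 1.00 |

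**Step 3, direction.** Here a scale must be assumed: symmetric, 7 points, coded −3 to +3. There are 7 × 7 = 49 possible pairs (b, v). A reversal means that v and v − b have opposite signs.
- For v > 0 and v − b < 0 we need b > v > 0. The pairs are (2, 1), (3, 1) and (3, 2), which makes 3.
- The mirror images give 3 more. Total 6 of 49 (12.2%).
- With b within one step of neutral there are 3 × 7 = 21 pairs. A reversal needs b of at least 2 in size, so the count is 0 of 21.
- With b = 0 the count is 0 of 7.

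These count possible pairs. They are not expected frequencies.

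**The case against.** The strongest objection is that the form itself cannot be seen. Protocol 8.6 refers to Appendix G, where the question, categories and reference period would stand, and only its heading survives in this copy. If the item rates current severity, as Protocol 5.1 says and the Synopsis arguably says, change from baseline is the right endpoint. Collecting it twice before dosing fits that reading. If instead the question refers back to screening, the difference would remove drift before dosing. This objection stands: the point is conditional on the form.

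Second, the SAP already summarises the visit value by cohort at Weeks 6 and 13 and lists the scores. SAP 4.0 already provides counts and percentages for categorical data, and SAP 6.7.2 already applies the full analysis set and the per protocol set. The rating will therefore be reported either way. This also stands and keeps the point small. It does not settle which summary is the named endpoint.

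Third, arithmetic subtraction is a reading of the text. SAP 6.7.1.6 also uses change from baseline for categorical findings such as reflexes. The word score in the PGI-C paragraph makes subtraction the natural reading, but the text does not spell it out.

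Two stronger readings are tempting. A reader might infer that the plan omits the reference point. The documents do not support that, because Appendix G is cited and its content is simply not in this copy. A reader might also count every pair in which the signs of v and v − b differ, which gives 18 of 49 on the assumed scale, and call them all disagreements in direction. Of those, 12 involve a zero (6 with v = b ≠ 0, and 6 with v = 0 and b ≠ 0) and are not reversals.

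**Conclusion.** The point holds in conditional form and is minor. By the item's name and by its description in Protocol 8.6 and the SAP, the endpoint as written is a difference between two change ratings. If Appendix G confirms a change rating, the difference either repeats the post-dose answer or mixes it with the pre-dose answer. The cohort mean moves by 0.17 step for each subject one step off neutral, from 0 to at most 1.00 if all six are one step off in the same direction. Outright reversals need a pre-dose answer at least two steps from neutral; on the assumed 7-point scale they make up 6 of 49 possible pairs.

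The result rests on three assumptions: that the form rates change, unit-step coding with complete data, and, for the reversal count only, the scale length. PGI-C is one of six listed exploratory endpoints and is analysed descriptively. It would be wrong to infer that the subjects' reports are lost or that a study conclusion is at risk.

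**What to change.** Low priority. Check the form in Appendix G, then take one of two routes.

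1. **If it rates change.** Make the Week 6 and Week 13 rating the named endpoint, shown as n and % per response category by cohort in the full analysis set and the per protocol set, with the non-missing denominator of SAP 4.0. Remove change from baseline for PGI-C from the Protocol Synopsis, Protocol 8.6, the SAP 6.7.2 endpoint list and the SAP PGI-C paragraph, as a stated exception to the default in Protocol 8. Keep the pre-dose ratings in the listings. If only the SAP is amended, record the departure in SAP 9.0.
2. **If it rates current severity.** Keep change from baseline, and correct the description in Protocol 8.6 and the SAP paragraph to match the Synopsis and Protocol 5.1.

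The cost is very small: on the first route one category table replaces the change table and some wording changes; on the second only wording changes. No new data are needed.
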